##### **Potential Benefits**

Individuals receiving study medication may experience a reduction in or discontinuation of their alcohol consumption, which may improve their health and well-being. Subjects will also receive close psychiatric and medical attention, including careful evaluation of their medical and psychiatric status. The potential benefits to society include a potential improvement in the effectiveness of treatment for problem drinking, which may reduce the personal and societal costs associated with the problem.

CONFIDENTIAL

This material is the property of the University of Pennsylvania. Do not disclose or use except as authorized in writing by the study sponsor

## Risk Benefit Ratio

The potential benefits of this study far outweigh the potential risks. Alcohol use disorders are serious disorders with mildly effective pharmacotherapy. Even in the best programs, relapse rates are high. Individuals accepted into this study will receive close medical and psychiatric monitoring. Subjects will be screened prior to admission into the study and those at risk for adverse reactions will be excluded. Subjects selected for participation will be monitored closely for adverse effects of topiramate.

## 2 Study Objectives

**Objective 1** Pilot cue sets (see Appendix 1) and confirm brain and behavioral responses to alcohol cues in individuals with AUD using pCASL fMRI

**Hypothesis 1:** Similar to our other pCASL fMRI cue-reactivity studies in drug-dependent individuals, subjects will exhibit greater brain activity in the interconnected VS and medial orbitofrontal cortex (mOFC) during alcohol cue exposure compared to non-alcohol cue exposure.

**Objective 2a** Demonstrate neuromodulatory effects of a GABA/glutamate modulator, topiramate, on RB and alcohol cue reactivity

**Hypothesis 2a:** We hypothesize that topiramate will ameliorate neurophysiological vulnerabilities by dampening neural activity in the brain 'at rest' and during alcohol cue exposure in reward-related regions, such as the amygdala, mOFC, VS, and the insula. In contrast, neural activity in placebo-treated individuals at rest and in alcohol cue reactivity will not differ from pre- to post-treatment.

**Objective 2b** Examine the mechanism underlying topiramate's ability to blunt alcohol cue reactivity and reduce heavy drinking days

**Hypothesis 2b:** We hypothesize that there will be a direct relationship between RB in the VS and mOFC and its effects on alcohol cue reactivity. Although overall effects are expected, reductions in heavy drinking days will correlate with topiramate's ability to modulate reward circuitry responses.

**Exploratory Objective** Examine the moderating effects of rs2832407 on topiramate's effects on brain and behavioral responses

**Exploratory hypothesis:** C-allele homozygotes at this locus will show the most robust effects of topiramate.

## 3 Study Design

### 3.1 General Design

- **Phase IV Study** - This is a phase IV research study aimed at identifying the brain and behavioral mechanisms underlying the GABA/glutamate modulator, topiramate.
- **Design** – Heavy drinkers who meet DSM-5 criteria for AUD and express an interest in reducing or stopping drinking will be recruited, screened, consented, and if eligible, will complete a randomized double-blind, placebo-controlled study of topiramate ( $N=40$ ; topiramate 200 mg/day:  $n=20$  or placebo:  $n=20$ ). Topiramate or placebo will be initiated after Scan 1 and continued with weekly visits and medical management [33]. During the 7th week, participants will complete Scan 2 followed by medication taper and an endpoint visit. We will use perfusion fMRI during alcohol cue exposure to acquire brain and behavioral responses to alcohol cues. The goals of this study are to pilot test the validity of our alcohol cues and to identify brain and behavioral mechanisms of topiramate in reducing heavy drinking in alcohol dependent individuals.
- **Study Duration** – The duration of this study will be approximately 9 weeks, including screening, Scan 1, 8 weeks of medication and medical management (including medication taper), Scan 2 during week 7, medication taper, and an endpoint visit. The entire study will run for approximately 24 months.

CONFIDENTIAL

This material is the property of the University of Pennsylvania. Do not disclose or use except as authorized in writing by the study sponsor

### **3.2 Primary Study Endpoints**

The primary endpoints to be measured include:

- Self-report ratings of cues, subjective ratings of craving during/following cue exposure, and neuroimaging data on cerebral blood flow when the brain is at rest and when exposed to alcohol cues.

### **3.3 Secondary Study Endpoints**

The effects of rs2832407 on topiramate's neural mechanisms

## **4 Subject Selection Subject Selection and Withdrawal**

### **4.1 Inclusion Criteria**

- 1) Physically healthy, as determined by a comprehensive physical examination and approval of the study physician males or females who drink alcohol, ages 18-60.
- 2) Have an average weekly ethanol consumption of  $\geq 24$  standard drinks for men, or  $\geq 18$  standard drinks for women [34].
- 3) Females must be non-pregnant, non-lactating and either be of non-childbearing potential (i.e. sterilized via hysterectomy or bilateral tubal ligation or at least 2 years post-menopausal) or of child bearing potential but practicing a medically acceptable method of birth control. Examples of medically acceptable methods for this protocol include: the birth control pill, intrauterine device, injection of Depo-Provera, Norplant, contraceptive patch, contraceptive ring, double-barrier methods (such as condoms and diaphragm/spermicide), male partner sterilization, abstinence (and agreement to continue abstinence or to use an acceptable method of contraception, as listed above, should sexual activity commence), and tubal ligation.
- 4) Provide voluntary informed consent.
- 5) Must be able to read. [Subjects are required to be able to read because there are several self-administered measures that they must read, understand and provide written answers.]
- 6) Intelligence quotient of  $\geq 80$ , as estimated by the 2-subtest score of the Wechsler Abbreviated Scale of Intelligence (WASI) [35].

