## **1.3 *Precinical Data***

### Drug-Drug Interactions and Precautions

CONFIDENTIAL

This material is the property of the University of Pennsylvania. Do not disclose or use except as authorized in writing by the study sponsor

Topiramate may have interactions with some antiepileptic drugs and oral contraceptives. Specifically, concomitant use of topiramate with standard antiepileptic drugs (i.e., Phenytoin, Carbamazepine, Valproic acid, and Lamotrigine) has been shown to decrease plasma levels of topiramate. Topiramate may also reduce the efficacy of some hormonal contraceptives (birth control pills, hormonal implants, or hormonal injections). Topiramate does not produce clinically significant additive central nervous system depressant effects in combination with ethanol. Concomitant use of topiramate with other carbonic anhydrase inhibitors (e.g., zonisamide, acetazolamide, or dichlorphenamide) may increase severity of metabolic acidosis and may also increase the risk of kidney stone formation. There is no evidence that topiramate has carcinogenic, teratogenic, or mutagenic potential. Further, topiramate is not reinforcing and is therefore not a drug of abuse.

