### **4.2 Exclusion Criteria**

- 1) A current, clinically significant physical disease or abnormality on the basis of medical history, physical examination, or routine laboratory evaluation.
- 2) History of head trauma or injury causing loss of consciousness, lasting more than five (5) minutes or associated with skull fracture or inter-cranial bleeding or abnormal MRI.
- 3) Current major DSM-IV Axis I diagnoses other than alcohol, nicotine, and cannabis use disorders.
- 4) Presence of magnetically active irremovable prosthetics, plates, pins, permanent retainer, bullets, etc. (unless a radiologist confirms that its presence is unproblematic).
- 5) History of a serious psychiatric illness including psychosis, bipolar disorder, or suicidal or homicidal intent.
- 6) Current treatment with carbonic anhydrase inhibitors, due to the added risk of metabolic acidosis.
- 7) Claustrophobia or other medical condition preventing subject from lying in the MRI for approximately one (1) hour.
- 8) Current regular treatment with psychotropic medications (e.g., benzodiazepines, antidepressants), which affect neurotransmitter systems or a medication being used to treat alcohol use disorders (e.g., naltrexone, acamprosate).
- 9) Vision problems that cannot be corrected with glasses.
- 10) Body Mass Index (BMI) greater than or equal to 34, body girth greater than 52 inches and a head girth greater than 25 inches [Imaging data acquisition is impaired with high weight individuals].

CONFIDENTIAL

This material is the property of the University of Pennsylvania. Do not disclose or use except as authorized in writing by the study sponsor

- 11) Individuals suffering from or with a history of stroke and/or stroke related spasticity.
- 12) History of glaucoma or kidney stones.
- 13) Individuals who are HIV positive, as the human immunodeficiency virus affects the brain.
- 14) Individuals with a history of seizures.
- 15) Individuals who have taken topiramate for alcohol use disorder and report no treatment response.

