### **4.4 Early Withdrawal of Subjects**

#### **4.4.1 When and How to Withdraw Subjects**

Subjects with severe psychological symptoms (e.g., suicidal thoughts), those who fail to adhere to protocol requirements, and those withdraw consent will be withdrawn from the study and if applicable, referred for appropriate clinical care. If a subject is found to be pregnant during screening or during study, she will immediately be withdrawn from the study, referred for obstetric evaluation, and advised to discontinue all drinking.

Any subject experiencing a serious adverse event felt to be related to study drug should be withdrawn from the study.

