#### **6.4 Weekly Visits (approximately 50 minutes)**

At each weekly visit, subjects in both medication groups will receive medical management (MM) [33]. This provides a basic clinical intervention that was designed to be used in conjunction with prescribed medication, and to be easily implemented by medically trained practitioners in non-specialty settings. The treatment will support subjects' efforts to reduce their drinking.

The first session (conducted right after the first MRI scan) will consist of a review of the results of the initial evaluation, identifying any medical concerns. This session will also use the brochure *A Guide to Sensible Drinking*, developed for use in the World Health Organization Brief Intervention Study project. The subject is then provided with a rationale and information about pharmacotherapy and the importance of adherence. At each visit, assessment and counseling (lasting approximately 15 minutes) are conducted. During these sessions, the nurse will perform a medical check on the subject's general functioning, obtain vital signs and weight, ask about medication side effects and concurrent medications, monitor the subject's medication adherence, and as appropriate, make recommendations on strategies for medication adherence for the subject to follow until the next visit. Men will be advised to consume no more than 4 standard drinks per day and 12 standard drinks per week and women will be advised to consume no more than 3 drinks per day and 8 drinks per week. Because subjects will not be physically dependent on alcohol, reduction of heavy drinking is a safe and ethical goal. The research technician or coordinator will measure the subject's breath alcohol concentration, perform a brief assessment of the subject's drinking, review the self-administered BDI to assess suicidal thoughts/ideation (and discuss with the nurse and/or physician, if there is endorsement of suicidal thoughts). For patient safety during travel, subjects will be instructed not to drink prior to study visits. At each visit, the subject's BrAC, weight, and vital signs will be measured. Subjects must have a breath alcohol level of 0.00 g% to complete the screening visit, 2 lab MRI scan visits, and endpoint visit, and below 0.05 g% to complete the weekly study visits. Study staff will follow TRC standard operating procedures for all subjects that present with a breath alcohol level above 0.00 g% at study visits.

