### **Schedule of Assessments**

Instrument	Visit 0 Screening	Visit 1 MRI	Visits 2-6	Visit 7 MRI	Visit 8	Visit 9 Endpoint
Breath Alcohol Concentration & Vital signs	X	X	X	X	X	X
Study Overview & Informed Consent	X					
Medical History & Physical Exam	X					
Laboratory tests (Blood for CBC, GGTP, HIV and DNA)						X (GGTP only)
MRI video	X					
MRI safety sheet (metal)	X	X		X		
Urine pregnancy test	Females	Females		Females		
Urine drug toxic screen	X	X		X		
Blood sample (2 Tbsp)	Females	Females		Females		
Demographic interview	X					
Structured Clinical Interview for DSM	X					Alcohol Module Only
Wechsler Abbreviated Scale of Intelligence	X					
Timeline Follow-Back Interview	X	X(brief)	X(brief)	X(brief)	X(brief)	X(brief)
Beck Depression Inventory	X	X	X	X	X	X
Short Index of Problems	X			X		X

CONFIDENTIAL

This material is the property of the University of Pennsylvania. Do not disclose or use except as authorized in writing by the study sponsor

Fagerstrom Test of Nicotine Dependence	X					X
Obsessive Compulsive Drinking Scale	X	X		X		X
Alcohol Urge Questionnaire	X	X		X		X
Within Session Rating Scale		X		X		
Clinical Institute Withdrawal Assessment for Alcohol Scale	X	X		X		
CogBias Tasks		X		X		
Cogstate Battery		X		X		X
Controlled Oral Word Association test		X		X		
Digit Span		X		X		
Medical Management		X	X	X	X	X
Endpoint/Termination Form						X
Medication Questionnaire						X
Measures of Treatment		X	X	X	X	X

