### **8.6 Protection of Subjects**

Complementing the safety measures noted above, additional procedures will be followed to protect the safety of the research subjects. Potential Subjects will be screened for medical illnesses that would preclude the use of topiramate. Subjects selected for the study will be evaluated weekly while receiving study drug treatments. AEs will be monitored weekly and a study physician will be available at all times to evaluate and treat adverse effects of the medication. On a weekly basis weights and vital signs will be obtained.

CONFIDENTIAL

This material is the property of the University of Pennsylvania. Do not disclose or use except as authorized in writing by the study sponsor

Significant AEs will result in exclusion from the study. Venipuncture will be carried out with good aseptic technique by an experienced phlebotomist, nurse, or physician. Venipuncture sites will be monitored carefully for signs of infection. At the conclusion of randomized medications, a physical examination, STUDY LABORATORY TESTS, and a urine pregnancy test (if female of childbearing capability) will be performed. Subjects will be given a 24-hour emergency number they can call if necessary. The PI or study psychiatrist will clinically follow all subjects who are discontinued due to a serious AEs until the AE resolves and becomes completely stable, unless a referral to another physician (i.e. specialist) is clinically indicated or requested by the subject.

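### The protocol warns that topiramate may weaken pills, implants and injections, yet accepts each of these alone as adequate contraception

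*Combined protocol and SAP*

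**What the plan says.** Section 1.3 (Drug-Drug Interactions and Precautions) states: "Topiramate may also reduce the efficacy of some hormonal contraceptives (birth control pills, hormonal implants, or hormonal injections". It gives no dose and no size of effect.

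Section 4.1, criterion 3, requires a woman of childbearing potential to practise one acceptable method. The list opens: "Examples of medically acceptable methods for this protocol include: the birth control pill, intrauterine device, injection of Depo-Provera, Norplant, contraceptive patch, contraceptive ring". It continues with double-barrier methods, partner sterilisation, abstinence and tubal ligation. Barrier methods are offered as one option among the others, not as an addition to a hormonal method.

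Two later provisions deal with a pregnancy once it exists. Section 4.4.1 says: "If a subject is found to be pregnant during screening or during study, she will immediately be withdrawn from the study". The Schedule of Assessments has a row headed "Urine pregnancy test", marked for females at Visits 0, 1 and 7, and section 8.6 adds a test when randomised medication ends.

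**The concern.** The protocol identifies an interaction that bears directly on one of its own entry conditions and does not carry it into that condition. Staff who apply criterion 3 exactly will enrol a woman whose only contraception is of a type the study drug may make less effective, and nothing in the visit procedures prompts them to act.

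The protocol plainly intends to avoid pregnancy on study drug: contraception is a condition of entry, and a pregnant participant is withdrawn at once, referred for obstetric evaluation and advised to stop drinking. The testing and withdrawal rules detect a pregnancy; they do not prevent one. No claim of fetal harm is made here, because section 1.3 reports no evidence that topiramate is teratogenic.

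**Working it through.** There is no planned figure to reproduce. The check is a comparison of text, with some simple counting for scale.

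**Step 1: match the warning to the criterion.**

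| Type named in 1.3 | Entry in criterion 3 | Condition attached |
|---|---|---|
| Birth control pills | Birth control pill | None |
| Hormonal implants | Norplant | None |
| Hormonal injections | Depo-Provera | None |

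All three flagged types are accepted, each alone. The patch and ring are also accepted. Section 1.3 does not name them, so the documents leave their status open.

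**Step 2: look for a back-up rule elsewhere.**
- 4.2 (exclusions) and 5.6 (prior and concomitant therapy): nothing on contraception.
- 6.2, 6.3 and 6.5 (screening and scan visits): pregnancy tests, but no check of method.
- 6.4 (weekly visits): the nurse will "ask about medication side effects and concurrent medications". Contraceptive method is not mentioned.
- 8.6: at the end of medication, "and a urine pregnancy test (if female of childbearing capability) will be performed". This is detection only, and it does not appear in the Schedule of Assessments.

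**Step 3: compare with other interactions in the same section.** Taking topiramate with other carbonic anhydrase inhibitors "may increase severity of metabolic acidosis". That is hedged in the same way, yet it became exclusion 6: "Current treatment with carbonic anhydrase inhibitors, due to the added risk of metabolic acidosis". The parallel is useful but not uniform. Section 1.3 also describes antiepileptic drugs lowering topiramate levels, and no exclusion names that interaction; exclusions 8 (psychotropic medication) and 14 (seizure history) would catch some of those patients indirectly. The comparison shows that hedged wording did not stop the authors from writing a rule. It does not show that every other warning became one.

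**Step 4: scale.**
- Time on drug (Table 1): 7 weeks × 7 days + taper of (2 + 2 + 2) days = 49 + 6 = 55 days, if the schedule is kept.
- Longest interval without a scheduled pregnancy test: Visit 1 to Visit 7 = 6 weekly intervals × 7 = 42 days. It spans Visits 2 to 6 (five visits) while the daily dose rises from 25 to 200 mg.
- Listed examples: pill, IUD, Depo-Provera, Norplant, patch, ring, double-barrier, partner sterilisation, abstinence, tubal ligation = 10. Flagged in 1.3: 3. Not flagged: 10 − 3 = 7, or 7 − 2 = 5 if the patch and ring were treated like the flagged three. The list is of examples only, so these counts show that alternatives exist and nothing more.
- Upper bound on those exposed: the planned topiramate arm is 20, men and women together (5.3). The documents give neither the number of women nor their methods, so no count of pregnancies can be offered.

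The pilot sub-study repeats the same list (14.4.1) but gives no study drug, so the point concerns the main study only.

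**The case against.** The strongest case against is that this is a small drafting gap of unproven consequence. The warning says only that efficacy may fall for some hormonal methods. Nothing shows that the effect occurs at 200 mg/day or during titration, and the same section reports no evidence of teratogenicity. The carbonic anhydrase rule also differs in kind: it guards against a direct toxicity listed under Potential Risks in section 1.5, where contraceptive interaction does not appear. Criterion 3 speaks of medically acceptable methods and gives examples, which leaves room for judgement; the study physician approves entry and the principal investigator signs off the criteria; and the weekly question on concurrent medication could pick up a pill or an injection. Finally, the consent form is not in the review copy and may tell women to add a barrier method.

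Much of this stands. The size of the interaction is not established, the parallel is imperfect, and the test interval concerns detection rather than prevention. If the consent form does give that instruction, the practical gap narrows considerably.

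The text mismatch remains. Physician and investigator sign-off applies the very criterion that names these methods as acceptable for this protocol, so it gives no reason to question them. A nurse who learns that a participant takes the pill has no instruction about what to do next. A warning in the consent form would inform the participant but would not change who is eligible.

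**Conclusion.** The concern holds. Criterion 3 accepts, without condition, all three contraceptive types that section 1.3 says topiramate may make less effective, and no section available for review requires a back-up. It is best described as a precaution not carried into the rules, not as a logical contradiction.

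It should be fixed on participant-safety grounds. Exposure lasts up to 55 days in an unknown subset of a 20-person arm. Confidence is high that the texts do not match; the documents do not allow any estimate of how often harm would follow. The conclusion rests on two assumptions: that the protocol means contraception to be effective while women take study drug, which the entry and withdrawal rules support, and that no back-up requirement sits in the consent form, which could not be checked.

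**What to change.** Amend criterion 3 for the main study. A woman of childbearing potential who relies on the pill, an implant or an injection must either add a barrier method for as long as she takes study drug, or use a listed method that 1.3 does not flag, such as an IUD, double-barrier methods, partner sterilisation or tubal ligation. State explicitly whether the patch and ring fall under the same rule. Have the nurse confirm and record the method at screening and at each weekly visit, next to the existing question on concurrent medication. Check that the consent form says the same.

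The cost is one wording amendment and one line on the screening and weekly-visit forms, with no extra visits or tests. Some women will need counselling or an added method, and a few may not qualify.

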### **4.2 Exclusion Criteria**

- 1) A current, clinically significant physical disease or abnormality on the basis of medical history, physical examination, or routine laboratory evaluation.
- 2) History of head trauma or injury causing loss of consciousness, lasting more than five (5) minutes or associated with skull fracture or inter-cranial bleeding or abnormal MRI.
- 3) Current major DSM-IV Axis I diagnoses other than alcohol, nicotine, and cannabis use disorders.
- 4) Presence of magnetically active irremovable prosthetics, plates, pins, permanent retainer, bullets, etc. (unless a radiologist confirms that its presence is unproblematic).
- 5) History of a serious psychiatric illness including psychosis, bipolar disorder, or suicidal or homicidal intent.
- 6) Current treatment with carbonic anhydrase inhibitors, due to the added risk of metabolic acidosis.
- 7) Claustrophobia or other medical condition preventing subject from lying in the MRI for approximately one (1) hour.
- 8) Current regular treatment with psychotropic medications (e.g., benzodiazepines, antidepressants), which affect neurotransmitter systems or a medication being used to treat alcohol use disorders (e.g., naltrexone, acamprosate).
- 9) Vision problems that cannot be corrected with glasses.
- 10) Body Mass Index (BMI) greater than or equal to 34, body girth greater than 52 inches and a head girth greater than 25 inches [Imaging data acquisition is impaired with high weight individuals].

CONFIDENTIAL

This material is the property of the University of Pennsylvania. Do not disclose or use except as authorized in writing by the study sponsor

- 11) Individuals suffering from or with a history of stroke and/or stroke related spasticity.
- 12) History of glaucoma or kidney stones.
- 13) Individuals who are HIV positive, as the human immunodeficiency virus affects the brain.
- 14) Individuals with a history of seizures.
- 15) Individuals who have taken topiramate for alcohol use disorder and report no treatment response.
- 16) Current DSM-5 diagnosis of alcohol use disorder that is clinically too severe to permit them to participate in a research trial in which the goal is to stop or reduce drinking [Because there is no clear empirical basis for choosing a cutoff with respect to AUD criteria, we will exclude patients who, on clinical examination by a physician, are deemed to be too severely alcohol dependent to permit them to participate in a research trial. This determination will be based on evidence of adverse medical (e.g., gastritis) or psychiatric effects (e.g., depression with suicidal ideation). In addition, individuals with no recent evidence of the capacity to reduce drinking from very high levels of intake or a history or present evidence of significant alcohol withdrawal symptomatology will be excluded. (Significant withdrawal will be considered to be present when there is a history of substantial tremor, autonomic changes, perceptual distortions, seizures, delirium, or hallucinations or a report of drinking to avoid withdrawal symptoms or of prior treatment of withdrawal)].

